## 17.0 Trial closure

#### 17.1 End of trial

The end of the trial will be when the last participant has completed their one year follow-up, at which point the 'declaration of end of trial' form will be submitted to the REC by the ICNARC CTU.

## 17.2 Archiving trial documents

At the end of the trial, the ICNARC CTU will archive securely all centrally-held trial-related documents for a minimum of ten years in accordance with ICH GCP guidelines. Arrangements for confidential destruction of all documents will then be made. The Site PI will be responsible for archiving all trial-related documents (including CRFs and other essential documents) held at the participating site for a minimum of ten years after the end of the trial. Essential documents are those which enable both the conduct of the trial and the quality of the data produced to be evaluated and to show whether the unit complied with the principles of ICH GCP and other applicable regulatory requirements.

Guidance on archiving will be provided in the trial-specific SOP. All archived documents, held centrally and locally, should be available for inspection by appropriate authorities upon request.

## 17.3 Early discontinuation of the trial

The trial may be stopped early upon recommendation of the TSC. In which case, the ICNARC CTU will inform all relevant staff working on SCARF and advise on the actions to be taken as regards the treatment of participants. All randomised participants will continue to be followed up as per the SCARF Protocol.

# 18.0 Trial management and committees

#### 18.1 Good research practice

SCARF will be managed according to the Medical Research Council's (MRC) Guidelines for Good Research Practice, Guidelines for Good Clinical Practice in Clinical Trials and Procedure for Inquiring into Allegations of Scientific Misconduct. The ICNARC CTU has developed its own policies and procedures, based on these MRC guidelines, for the conduct of all its research activities. In addition, ICNARC has contractual confidentiality agreements with all members of staff. Policies regarding alleged scientific misconduct and breach of confidentiality are reinforced by disciplinary procedures.

## 18.2 Trial Management Group

All day-to-day management of SCARF will be the responsibility of the TMG. Members of the TMG will include the SCARF Trial Manager, the Chief Investigator and the clinical co-investigators. The TMG will meet regularly to discuss management and progress of the trial and findings from other related research.

## 18.3 Trial Steering Committee

The trial will be supervised by the TSC, which will be chaired by an independent member, [name], Paediatric Respiratory Physician, Royal Brompton Hospital & Harefield NHS Foundation Trust. The TSC will include at least two additional independent members and a service user representative.

## 18.4 Data Monitoring and Ethics Committee

The DMEC will be chaired by [name], Consultant Paediatric Intensivist, Guy's and St Thomas' NHS Foundation Trust, who is an experienced statistician and paediatric intensivist. All members of the DMEC will be independent of both the SCARF TMG and the TSC. The DMEC will operate under the DAMOCLES Charter, and will report to the TSC, making recommendations on the continuation, or not, of the trial. Safety will be monitored by the DMEC through mandatory reporting of SAEs throughout the trial period.

#### 18.5 Role of the ICNARC Clinical Trials Unit

The ICNARC CTU will be responsible for the day-to-day management of the trial and will act as custodian of the data. The ICNARC CTU will ensure that all SAEs are reported, as appropriate, to the REC.

## 19.0 Statistics

#### 19.1 Sample size calculation

Data submissions to the Paediatric Intensive Care Audit Network, the national clinical audit for PICUs in the UK, report a mean of 3.3 patients per month with severely impaired immunity admitted to GOSH PICU over the last eight years. Two thirds were admitted with respiratory failure as the primary reason for admission and 75% of these received mechanical ventilation. We estimate that a similar number experience acute respiratory distress on the ward fitting our inclusion criteria that do not require ICU admission. Therefore we would be expecting to randomise around 4-5 participants per month and anticipate an intubation rate of around 35-40% in the control group. Assuming the same relative risk reduction (~60%) as observed in adult studies, a sample of 148 children (74 in each group) is required to detect a reduction in intubation rate from 35% to 14% with 80% power and a type 1 error rate of 5% (two-sided).

## 19.2 Statistical analysis

All analyses will be conducted by intention to treat, with a two-sided p value of <0.05 taken to indicate a statistically significant result. The primary effect estimate will be the relative risk of intubation for invasive mechanical ventilation at 30 days post-randomisation, with statistical significance assessed by Fisher's exact test. As a secondary analysis, the primary outcome will also be analysed by multivariable logistic regression adjusted for baseline covariates of age, chronic diagnosis, bone marrow transplantation, suspected cause of acute respiratory failure, weight and PIM2 score . The baseline covariates have been selected *a priori* for their anticipated strong association with the outcome, no further selection of covariates will be performed based on imbalance at baseline or significance in univariable analyses. Secondary outcomes will be analysed by logistic regression for binary outcomes (mortality, requirement of level 2/3 respiratory support) or linear regression for continuous outcomes (PELOD , days free from ventilator support/supplemental oxygen) adjusted for the same baseline covariates as above. Due to the small sample size, no subgroup analyses are planned.

A single interim analysis will be conducted at 50% recruitment. The results of the interim analysis will be reviewed by the DMEC, using a Peto-Haybittle stopping rule (P<0.001) to recommend early termination of the trial due to harm^20. It is not recommended that the trial should terminate early for efficacy, as any treatment effect that would be statistically significant at this level would be sufficiently large as to be clinically implausible and therefore unlikely to change clinical practice. Additional interim analyses will be conducted if requested by the DMEC.

# 20.0 Ethical compliance

SCARF will be conducted in accordance with the approved Trial Protocol, ICH GCP guidelines, the Data Protection Act (1998), the Mental Capacity Act (2005), as well as the ICNARC CTU's research policies and procedures (see section 18.0).

The trial has received a favourable opinion from the London Riverside REC. The ICNARC CTU will submit annual progress reports and all amendments to the SCARF Protocol to the REC for review. The ICNARC CTU will provide relevant approved trial documents and other related materials to participating sites.

It is the responsibility of the Site PI to obtain the necessary local approvals for SCARF, including approval from the Trust Research & Development (R&D) Department. The Site PI should submit the current approved versions of the Trial Protocol, PIS, Consent Form, and any other written information to be given to participants, to the R&D Department. It is also the responsibility of the Site PI to inform the R&D Department of any subsequent revisions to the Trial Protocol or other trial documents. Evidence of NHS Trust R&D approval must be provided to the ICNARC CTU prior to recruitment of participants.

#### 20.1 Participant confidentiality and data protection

Identifiable participant data, including full name, date of birth and NHS number will be required by the ICNARC CTU to successfully follow-up participants. The ICNARC CTU will act to preserve participant confidentiality and will not disclose or reproduce any information by which participant could be identified. Data will be stored securely.

ICNARC is registered under the Data Protection Act (1998) and all ICNARC CTU staff have undergone data protection and ICH GCP training.

# 22.0 Funding

SCARF is funded by Great Ormond Street Hospital Children's Charity, Registered Charity No. 235825.

# 23.0 Publication policy

The final report, including a detailed description of the trial, results and recommendations for future policy and practice and future research, will be submitted

to the Great Ormond Street Hospital Children's Charity. Articles will be prepared for publication in peer-reviewed scientific journals, as well as relevant professional journals. All participant data will be anonymised before publication.

# Appendix 1: Expected adverse events

Expected adverse events that could be observed in participants up to 30 days following randomisation:

- Pneumothorax
- Facial pressure sores
- Sinusitis
- New nosebleed
- Corneal irritation
- Headache
- Abdominal bloating/distension
- Aspiration

[This list is not exhaustive. If an adverse event, as defined in section 14.1, occurs this should be recorded and reported as described in section 14.0]

## Version history

Version number	Date	Summary of main changes from previous versions
1.0	22/09/2016	N/A

## Abbreviations

AE	adverse event
BiPAP	bilevel positive airway pressure
CPAP	continuous positive airways pressure
FiO 2	fraction of inspired oxygen
GOSH	Great Ormond Street Hospital for Children
HFHO	High Flow Humidified Oxygen
ICNARC	Intensive Care National Audit & Research Centre
ICU	intensive care unit
PELOD	Paediatric Logistic Organ Dysfunction score
PICU	paediatric intensive care unit
PICANet	Paediatric Intensive Care Audit Network
PIM2	Paediatric Index of Mortality version 2
SAE	serious adverse event
ScvO 2	central venous oxygen saturation
SpO 2	oxygen saturation

## **1. Background**

The randomised study of early continuous positive airways pressure in acute respiratory failure in children with impaired immunity (SCARF) is a pragmatic, open, randomised controlled trial in infants and children with severely impaired immunity and acute respiratory failure.

This document describes the proposed statistical analyses for the Trial. It is important to set these out and agree on them in advance of analysing the outcome data for the Trial, so that data-derived decisions in the analyses are avoided.

## **2. Objective and hypotheses**

The primary objective of the Trial is to determine if admission to the paediatric intensive care unit (PICU) for early delivery of continuous positive airways pressure (CPAP) – i.e. before it is required to maintain gas exchange – reduces the requirement for invasive mechanical ventilation and improves survival in infants and children with severely impaired immunity and acute respiratory failure compared to standard care. The secondary objectives include comparing mortality at 30 days, 90 days and one year between the two treatment groups.

The hypothesis of the Trial is that early admission to the (PICU) for early delivery of CPAP will reduce the need for intubation and invasive mechanical ventilation within 30 days and improve survival from both acute and acute on chronic respiratory failure in children with impaired immunity.

## **3. Study design**

### **3.1 Inclusion/exclusion criteria**

The Trial population will consist of infants and children receiving treatment at a participating site who fulfil all of the inclusion criteria and none of the exclusion criteria below.

#### **3.1.1 Inclusion criteria**

- Age less than 18 years
- Expected to have impaired immunity for at least three months as a result of a primary diagnosis, therapy or a combination of both
- Acute respiratory failure or acute on chronic respiratory failure

#### **3.1.2 Exclusion criteria**

- Already receiving invasive mechanical ventilation for non-respiratory indications
- Other acute indication for emergency PICU admission and invasive mechanical ventilation, independent of the degree of respiratory failure (e.g. shock, reduced level of consciousness, seizures), as assessed by the PICU team
- Recent oesophageal/gastric surgery
- End-of-life care plan in place with limitation of resuscitation
- Life expectancy less than 12 months

- Already receiving treatment on PICU

## **3.2 Study Treatment**

The treatments used in the Trial are described below.

### **3.2.1 Intervention group**

Participants allocated to the intervention group (early CPAP) will be admitted to the PICU and receive CPAP of at least 6cm H2O with supplemental oxygen for a minimum of 12 hours per day for at least four consecutive days (Level 2 respiratory support). The interface for delivering CPAP (i.e. via face mask, helmet or infant flow-driver) will be at the discretion of the clinical team responsible for the participant's care. All other care will be determined by the clinical team primarily responsible for the participant's care.

### **3.2.2 Control group**

Participants allocated to the control group (usual treatment) will remain on the ward and receive supplemental oxygen to maintain oxygen saturation in accordance with standard local practice (Level 1 respiratory support). All other care (including antimicrobial therapy, fluid therapy, analgesia and sedative agents, bronchodilator therapy) will be determined by the clinical team primarily responsible for the child's care. Participants in the control group will be admitted to the PICU in accordance with standard acutely ill child protocols and as deemed necessary by the ICU outreach/Medical Rapid response teams and the clinical team responsible for the child's care.

### **3.2.3 Levels of respiratory support**

The four levels of respiratory support are as follows:

- i. Level 1: inspired oxygen therapy on the ward (control group only);
- ii. Level 2: CPAP at 6-10cm H2O;
- iii. Level 3: non-invasive bilevel positive airway pressure (BiPAP) via facemask or helmet;
- iv. Level 4: intubation and mechanical ventilation.

## **3.3 Outcome measures**

### **3.3.1 Primary**

The primary outcome measure is the requirement for intubation and invasive mechanical ventilation (Level 4 respiratory support) within 30 days post-randomisation

### **3.3.2 Secondary**

The secondary outcome measures are:

- maximum and aggregate paediatric logistic organ dysfunction score (PELOD) at 30 days post-randomisation;
- mortality at 30 days post-randomisation;
- requirement for Level 2 or Level 3 respiratory support within 30 days post-randomisation;
- days free from any ventilator support (Level 2, 3 or 4 respiratory support) at 30 days post-randomisation;

- days free from supplemental oxygen (i.e. above pre-acute respiratory failure requirement) at 30 days post-randomisation;
- hospital mortality;
- mortality at 90 days post-randomisation; and
- mortality at one year post-randomisation.

#### **4. Sample size calculation**

Data submissions to the Paediatric Intensive Care Audit Network (PICANet), the national clinical audit for PICUs in the UK, reported a mean of 3.3 patients per month with severely impaired immunity admitted to GOSH PICU over an eight-year period (2003-10). Two thirds were admitted with respiratory failure as the primary reason for admission and 75% of these received mechanical ventilation. We estimated that a similar number experience acute respiratory distress on the ward fitting our inclusion criteria that do not require ICU admission. Therefore we expected to randomise around 4-5 participants per month and anticipated an intubation rate of around 35-40% in the control group. Assuming the same relative risk reduction (~60%) as observed in adult studies, a sample of 148 children (74 in each treatment group) was required to detect a reduction in intubation rate from 35% to 14% with 80% power and a type 1 error rate of 5% (two-sided).

At the Trial Steering Committee meeting in November 2014, the decision was taken, due to poor recruitment, to continue the study to the current planned end of patient recruitment (January 2016) but not to seek additional funding to extend recruitment beyond this date.

#### **5. End of trial**

The end of the trial will be when the last participant has completed their one year follow-up.

#### **6. Analysis principles**

All analyses will be conducted by intention to treat. The patients will be analysed according to the treatment group they were randomised to, irrespective of whether the treatment allocated was received i.e. all patients will be included in the analysis, regardless of whether they have, or have not, adhered to the protocol. A two-sided p value of <0.05 will be taken to indicate a statistically significant result.

#### **7. Handling of missing data**

As the amount of missing data is anticipated to be minimal, a sensitivity approach will be taken when the primary outcome variable is missing. The primary analysis will be repeated once assuming that all patients allocated to early CPAP with missing outcomes did not receive invasive mechanical ventilation (Level 4 respiratory support), and all patients allocated to standard treatment with missing outcomes did receive invasive mechanical ventilation (Level 4 respiratory support). The analysis will then be repeated again with the opposite assumptions. This will then give the absolute range of how much the results could change if the primary outcome variable were complete.

In adjusted analyses missing baseline data will be handled by multiple imputation using chained equations.

## **8. Initial descriptive analyses**

### **8.1 Recruitment, treatment allocation and follow-up**

Recruitment to the Trial, treatment allocation and completeness of follow-up will be illustrated by a CONSORT flow diagram. All participating sites have maintained a Screening Log of infants and children who are eligible (fulfil all of the inclusion criteria and none of the exclusion criteria) but not randomised, or who fulfil all of the inclusion criteria but meet one or more of the exclusion criteria. Reasons for non-recruitment will be categorised and summarised.

### **8.2 Baseline characteristics**

The following baseline (pre-randomisation) demographic and clinical factors will be summarised by treatment group but not subjected to statistical testing:

- Age group (<12 months; ≥12 months)
- Age in months
- Gender
- Weight
- Acute respiratory failure or acute on chronic respiratory failure
- Bone marrow transplant
- Cause(s) of impaired immunity
- Suspected cause of acute respiratory failure (at the time of randomisation)
- PIM2r score
- Supplemental O2 requirement (pre-acute respiratory failure)

Numbers and percentages within each treatment group will be reported for categorical factors; means (with SD) and medians (with IQR) within each treatment group will be reported for continuous factors. P values will not be calculated or quoted.

### **8.3 Clinical management**

Clinical management will be summarised by treatment group but not subjected to statistical testing.

The treatment groups will be compared for the following:

- Admitted to PICU
- Length of stay in PICU
- CPAP (Level 2 respiratory support) received
- Length of stay in acute hospital (from randomisation)

Numbers (%) or means (SD) and medians (IQR), as appropriate, will be given in each treatment group. P values will not be calculated or quoted.

## 8.4 Protocol adherence

Numbers and percentages of protocol deviations will be reported. The following protocol deviations will be reported for the intervention (early CPAP) group:

- Did not start CPAP within 24 hours
- CPAP not received for specified time period (other than due to escalation of respiratory support)
- Higher level of respiratory support received without clear clinical criteria documented for escalation
- High Flow Humidified Oxygen (HFHO) received

The following protocol deviations will be reported for the control (usual treatment) group:

- Higher level of respiratory support received without clear clinical criteria documented for escalation
- High Flow Humidified Oxygen (HFHO) received

Overall adherence will be reported as the number and percentage of patients in each treatment group not meeting any of the above criteria.

## 9. Primary analysis

The number and percentage of patients requiring invasive mechanical ventilation 30 days following randomisation will be reported. Invasive mechanical ventilation by 30 days following randomisation will be compared between the treatment groups, unadjusted, using Fisher's exact test and reported as a relative risk with 95% confidence interval and as an absolute risk reduction with 95% confidence interval.

As a secondary analysis, the primary outcome will also be analysed using logistic regression adjusted for the following baseline covariates: age, weight, bone marrow transplantation and PIM2 score. Other covariates originally planned for inclusion in the adjusted analysis (cause of impaired immunity, suspected main cause of acute respiratory failure) will not be included in the model due to the smaller sample size. The results of the logistic regression model will be reported as an adjusted odds ratio with a 95% confidence interval. The unadjusted odds ratio will be presented for comparison.

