## 10. Secondary analyses

The subsequent secondary analyses will be adjusted using the following baseline covariates: age, weight, bone marrow transplantation and PIM2 score. The baseline covariates have been selected *a priori* for their anticipated strong association with the outcome. No further selection of covariates will be performed based on imbalance at baseline or significance in univariable analyses.

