## **12. Interim analyses**

A single interim analysis was planned to be conducted at 50% recruitment. The results of the interim analysis were to be reviewed by the DMEC, using a Peto-Haybittle stopping rule ( $P < 0.001$ ) to recommend early termination of the trial due to harm. However, as the required number of patients was not fulfilled, the interim analysis could not be carried out.

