Days free from supplemental oxygen at 30 days*, mean (SD)	XX.X (XX.X)	XX.X (XX.X)	Mean difference: X.X (X.X, X.X)	0.XXX
			Adjusted mean difference: X.X (X.X, X.X)	0.XXX
Hospital mortality, n (%)	XX (XX.X)	XX (XX.X)	Odds ratio: X.XX (X.XX, X.XX)	0.XXX
			Adjusted odds ratio: X.XX (X.XX, X.XX)	0.XXX
Mortality at 90 days*, n (%)	XX (XX.X)	XX (XX.X)	Odds ratio: X.XX (X.XX, X.XX)	0.XXX
			Adjusted odds ratio: X.XX (X.XX, X.XX)	0.XXX
Mortality at one year*, n (%)	XX (XX.X)	XX (XX.X)	Odds ratio: X.XX (X.XX, X.XX)	0.XXX
			Adjusted odds ratio: X.XX (X.XX, X.XX)	0.XXX

\*post-randomisation; n: number of patients; %: percentage of patients; SD: standard deviation

- v. Table 5a: Logistic regression model for requirement of invasive mechanical ventilation at 30 days post-randomisation

Variables	Odds ratio	95% CI	P-value
Treatment			
Usual treatment	1		
Early CPAP	X.XX	X.XX, X.XX	0.XXX
Age (per year)	X.XX	X.XX, X.XX	0.XXX
Weight (per 5kg)	X.XX	X.XX, X.XX	0.XXX
Bone marrow transplantation			
No	1		
Yes	X.XX	X.XX, X.XX	0.XXX
PIM2r score (per point)	X.XX	X.XX, X.XX	0.XXX

- vi. Table 5b: Linear regression model for maximum PELOD score at 30 days post-randomisation

Variables	Coefficient	95% CI	P-value
Constant	X.XX	X.XX, X.XX	0.XXX
Treatment			
Usual treatment	0		
Early CPAP	X.XX	X.XX, X.XX	0.XXX
Age (per year)	X.XX	X.XX, X.XX	0.XXX
Weight (per 5kg)	X.XX	X.XX, X.XX	0.XXX
Bone marrow transplantation			
No	0		
Yes	X.XX	X.XX, X.XX	0.XXX
PIM2r score (per point)	X.XX	X.XX, X.XX	0.XXX

- vii. Table 5c: Linear regression model for aggregate PELOD score at 30 days post-randomisation

Variables	Coefficient	95% CI	P-value
Constant	X.XX	X.XX, X.XX	0.XXX
Treatment			
Usual treatment	0		
Early CPAP	X.XX	X.XX, X.XX	0.XXX
Age (per year)	X.XX	X.XX, X.XX	0.XXX
Weight (per 5kg)	X.XX	X.XX, X.XX	0.XXX
Bone marrow transplantation			
No	0		
Yes	X.XX	X.XX, X.XX	0.XXX
PIM2r score (per point)	X.XX	X.XX, X.XX	0.XXX

viii. Table 5d: Logistic regression model for mortality at 30 days post-randomisation

Variables	Odds ratio	95% CI	P-value
Treatment			
Usual treatment	1		
Early CPAP	X.XX	X.XX, X.XX	0.XXX
Age (per year)	X.XX	X.XX, X.XX	0.XXX
Weight (per 5kg)	X.XX	X.XX, X.XX	0.XXX
Bone marrow transplantation			
No	1		
Yes	X.XX	X.XX, X.XX	0.XXX
PIM2r score (per point)	X.XX	X.XX, X.XX	0.XXX

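### The adjusted logistic models put five slopes on few events with no penalised method, so adjusted odds ratios will tend to be too extreme if CPAP works, and the Level 2/3 model may have no estimate

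*SAP*

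**What the plan says.** The primary comparison of intubation in SAP section 9 is Fisher's exact test, with an unadjusted relative risk and absolute risk reduction. As a secondary analysis the SAP adds "logistic regression adjusted for the following baseline covariates: age, weight, bone marrow transplantation and PIM2 score", and notes that "The unadjusted odds ratio will be presented for comparison". Cause of impaired immunity and suspected cause of respiratory failure, both in the protocol's model, "will not be included in the model due to the smaller sample size".

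Section 10 carries the set forward: "The subsequent secondary analyses will be adjusted using the following baseline covariates: age, weight, bone marrow transplantation and PIM2 score". In sections 10.1 and 10.2 this covers mortality at hospital discharge, 30 days, 90 days and one year, and requirement for Level 2 or 3 support. With intubation that makes six binary outcomes. Tables 5a, 5d, 5e and 5h to 5j give age, weight, bone marrow transplantation and PIM2 one coefficient each.

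On size, section 4 states that "a sample of 148 children (74 in each treatment group) was required" and records poor recruitment. Section 12 says of the look planned at 50% recruitment that "as the required number of patients was not fulfilled, the interim analysis could not be carried out". The final number of children is not stated. Neither document names a penalised or exact method, or says what happens if a model does not converge.

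**The concern.** Ordinary logistic regression, taken here to mean maximum likelihood, is biased away from no effect when events per coefficient are few and a true effect exists. With sparser data it can have no finite solution, because some combination of treatment and covariates predicts the outcome perfectly. The SAP recognises the size problem by dropping two covariates, but keeps the fitting method.

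Two things are at stake. If early CPAP works, the adjusted odds ratios in Table 4 will tend to look stronger than the truth. If a model fails, the analyst must choose a substitute after seeing the outcomes, which SAP section 1 says the document exists to prevent.

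**Working it through.** **Inputs from the documents.** Rates of 35% and 14%, 74 per group, two-sided 5%, 80% power, and a control rate of 35 to 40% (SAP section 4); interim at 50% (section 12); five slopes (Table 5a).

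**The plan's own figure.** With mean rate 0.245, n per group = [1.960·√(2·0.245·0.755) + 0.842·√(0.35·0.65 + 0.14·0.86)]² / 0.21² = 64.7. The continuity correction gives (64.7/4)·[1 + √(1 + 4/(64.7·0.21))]² = 73.9, so 74 per group and 148 in all. The stated size is reproduced.

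**Largest possible N.** 50% of 148 is 74, which was not reached, so N ≤ 73.

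**Expected intubations at N=73.**
- Design effect: 73 × 0.245 = 17.9, or 17.9/5 = 3.6 per slope.
- No effect: 73 × 0.35 = 25.6 to 73 × 0.40 = 29.2.

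**Simulation at 35% against 14%.** The documents do not give the following, so they are assumptions: age-weight correlation 0.9, bone marrow transplantation in 40%, and moderate covariate effects. There were 2,000 trials per row. The true covariate-adjusted log odds ratio is −1.33. Maximum likelihood (ML) means are over trials in which an estimate exists; percentages use unrounded values.

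| N | Expected events | Per slope | ML mean | Overstated | No estimate | Firth mean |
|---|---|---|---|---|---|---|
| 73 | 17.9 | 3.6 | −1.52 | 15% | 0.4% | −1.32 |
| 60 | 14.7 | 2.9 | −1.55 | 17% | 1.1% | −1.32 |
| 50 | 12.3 | 2.5 | −1.70 | 29% | 2.5% | −1.38 |
| 40 | 9.8 | 2.0 | −1.71 | 29% | 6.0% | −1.36 |
| 30 | 7.4 | 1.5 | −1.79 | 35% | 16.6% | −1.34 |
| 20 | 4.9 | 1.0 | −2.26 | 70% | 45.0% | −1.31 |

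This is not non-collapsibility. The unadjusted log odds ratio at these rates is ln[(0.14/0.86)/(0.35/0.65)] = −1.20, and the inflation is measured against the adjusted value of −1.33.

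A second simulation (true value −1.26) agrees. ML gives −1.44 at N=72 (1.44/1.26 = 1.14) and −1.56 at N=40 (1.56/1.26 = 1.24), with no estimate in 0.7%, 7% and 44% of trials at N=72, 40 and 20. Firth with the same covariates gives −1.27 and −1.30, lowers root mean squared error from 0.81 to 0.69 (N=72) and from 1.22 to 0.98 (N=40), and yields an estimate in at least 99.7% of trials.

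**No true effect (35% in both groups).** The mean ML log odds ratio is 0.02 at N=73 and −0.01 at N=40, so there is no inflation.

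**Age with weight.** At N=73, with age-weight correlation 0, 0.9 and 0.95, the median standard error of the treatment coefficient is 0.68, 0.69 and 0.69. Only the age coefficient loses precision (0.33, 0.77, 1.07).

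**Where failures for intubation come from.** The chance of no events in the CPAP group is 0.86³⁶ = 0.4% near N=72, 0.86²⁰ = 4.9% at N=40 and 0.86¹⁰ = 22% at N=20. At the larger sizes this explains most failures, and the unadjusted odds ratio fails with them.

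**Level 2 or 3 support.** Level 2 CPAP is the intervention (SAP section 3.2.1). If 97% of the CPAP group have the outcome (assumed), the chance that all do is 0.97³⁶ = 33% at N=73 and 0.97²⁰ = 54% at N=40. The simulation, with an assumed 40% in controls, finds no ML estimate in 33% and 55%. At 90% the chance that all do falls to 2% and 12%; at 100% an estimate never exists.

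**The case against.** The best defence is that little depends on these models. The adjusted intubation analysis is labelled secondary, and mortality and Level 2/3 support also get Fisher's exact test and an unadjusted relative risk. The two covariates removed have five and six categories in Table 1, so the SAP has already cut about nine parameters. The inflation depends on a large true effect: at 35% against 25% and N=72 the bias is only 0.04 on a log odds ratio of −0.52. It is also modest beside the noise: at N=73 it is 0.19 against a median standard error of 0.69, and the median ML estimate (−1.45) overstates less than the mean. All of this stands and limits the weight of the point.

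Fewer covariates would help as well. At N=72, cutting ordinary ML to treatment, age and transplantation reduces the mean bias from 0.19 to 0.07. In that comparison root mean squared error is 0.80 with five ML slopes, 0.70 with three, 0.66 with five Firth slopes and 0.63 with three. Firth therefore gains more without reopening the covariate list, which section 10 closes.

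A reader might infer more than the documents support:

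- *That 18 events is a ceiling.* It is an expectation under the design effect at the largest possible N, and the chance of more than 18 is 41%. It does not carry over to mortality: the case fatality of 20 to 50% cited in the protocol's Background would give 73 × 0.20 = 15 to 73 × 0.50 = 37 deaths.
- *That the intubation estimate will often not exist.* That holds only if N is far below 73, and the documents give no achieved N.
- *That including both age and weight is the cause.* The treatment coefficient is almost unaffected by their correlation.

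**Conclusion.** The point holds as a cheap improvement. Five slopes are fitted to six binary outcomes in at most 73 children, without a method suited to sparse events. If CPAP has the effect assumed at design, the adjusted log odds ratio for intubation is overstated on average by about 15% near N=72 and by roughly a quarter to 30% at N=40. Failure to obtain an estimate is rare near N=72, 6 to 7% at N=40 and about 45% at N=20. The Level 2/3 model is exposed at any size, to a degree that depends on how many of the CPAP group receive CPAP.

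The event counts follow from the documents. The inflation and failure rates also rest on the assumed covariate effects, the 97% and 40% for Level 2/3 support, and the reading of logistic regression as maximum likelihood. Nothing here touches the primary test or the unadjusted relative risk, and it gives no reason to expect a false positive when there is no effect.

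**What to change.** In SAP sections 9, 10.1 and 10.2, state that the adjusted analysis of every binary outcome uses Firth penalised logistic regression with profile-likelihood intervals, keeping age, weight, bone marrow transplantation and PIM2. Amend Tables 4, 5a, 5d, 5e and 5h to 5j to match. Because section 7 imputes missing baseline data, add a line on how the intervals are combined across imputations.

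The cost is one extra software routine and slight shrinkage towards no effect. For Level 2/3 support Firth solves only the computation: it gives a finite estimate, but an outcome that includes the allocated treatment remains hard to interpret.

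Dropping weight, splitting age at 12 months as in the minimisation, and adding a standardised relative risk and risk difference are optional.
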